4.5.4 Structural and mechanical integrity of the devices

Tables of absolute and relative frequencies will be presented to summarize the outcome of the visual inspection of the PI of the used devices regarding the structural/mechanical integrity and damage. The visual inspection performed by the PI targets the integrity of the syringe barrel and the completeness of the syringe. Summaries will be based on the number of ZLP-AI autoinjectors used and returned, based on the following categories:

- Device has no structural integrity issues and is not functionally compromised
- Device shows signs of structure integrity issues
- Device found to be functionally compromised
- Device has both structural integrity issues and found to be functionally compromised.

ZLP-AI deficiency as reported by the investigator will be summarized in frequency tables for all the auto-injectors used and returned to the clinic based on the following categories:

- Problem with packaging
- Inadequate labeling
- Inadequate instructions to use
- Problem with device preparation

- Problem with device deployment
- Problem with device removal
- Other.

Corresponding device information will be listed.

Of note, all used devices will be returned to UCB for an assessment of structural and mechanical integrity by the technical team. This source of information will not be captured in the study eCRF; thus, these assessments will be reported separately.

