
 
Evaluate the structural and mechanical integrity of the ZLP-AI after completion of self-administration
 
	
Other endpoint:
 
 
Occurrence of used ZLP-AI combination products identified as having structural or mechanical integrity issues after completion of self-administration.
 
Investigator observed and reported device deficiencies. Note: An independent assessment of the structural and mechanical integrity of all used ZLP-AI devices will additionally be performed by UCB. The outcome will be reported separately from the study results.
 

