### **6.1.1 Devices**

The ZLP-AI-1mL consists of the naked PFS (primary packaging containing ZLP drug product used for all Phase 3 studies and in the ZLP safety syringe 1mL) inside an auto-injector. The PFS volume will be administered from the same primary container, a 1mL long glass syringe, and a 29-gauge thin wall half inch stacked needle. The ZLP-AI-1mL is a single dose, disposable, nonsterile combination product.

Additional instructions for device use, including the injection angle, are provided in the IFU. Participants will be instructed to retain and return all ZLP-AI devices administered at home when they return to the clinic, as specified in the SoA (Section 1.3). Devices will be individually numbered for tracking purposes.

All device deficiencies (including malfunction use error and inadequate labeling) shall be documented and reported by the Investigator throughout the study (see Section 8.3.8) and appropriately managed by the Sponsor.

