### 8.1.2 Evaluation of post-use structural and mechanical integrity of ZLP-AI

The visual inspection of the used devices will check for structural/mechanical integrity and damage (ie, clear evidence of damage/compromised structural integrity and not any superficial, cosmetic imperfections). All evaluations will be performed by appropriately trained site staff.

All devices will be retrieved post-use and will be assessed for structural and mechanical integrity internally by the technical team at UCB. Results from the assessments will be reported as data on file.

The tests to be performed to assess structural and mechanical integrity of ZLP-AI are summarized in [Table 8-1](#).

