**Table 8-1: Summary table of structural and mechanical integrity tests**

Control	Methodology	Acceptance criteria
Integrity of the syringe barrel	Visual inspection	Attribute (pass/fail)
Syringe should be completely empty	Visual inspection	Attribute (pass/fail)
Locking mechanism that protects the needle is deployed and locked	Qualitative inspection	Attribute (pass/fail)

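### SAP 4.5.4 narrows two protocol device endpoints: its deficiency table counts only used and returned auto-injectors, and no study output is specified for the needle-lock control

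*SAP*

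**What the plan says.** **Protocol endpoints.** Table 3-1 lists two relevant items under other objectives. The first is confined to used devices: "Occurrence of used ZLP-AI combination products identified as having structural or mechanical integrity issues after completion of self-administration". The second is the device deficiencies that the investigator observes and reports, with no limit to used devices. Section 6.1.1 requires all deficiencies to be documented and reported throughout the study. Section 10.7.3 includes malfunctions, use errors and inadequate labelling in the definition. Section 9.4.2 plans a separate deficiency summary, again with no limit to used devices.

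**Protocol integrity tests.** Table 8-1 sets three pass/fail controls: "Integrity of the syringe barrel", "Syringe should be completely empty" and "Locking mechanism that protects the needle is deployed and locked". The method is visual inspection for the first two and qualitative inspection for the third. Section 8.1.2 first describes a visual inspection at the site ("All evaluations will be performed by appropriately trained site staff"), then an assessment of all devices by the sponsor's technical team, and then introduces the table. It does not say which of the two the table governs.

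**SAP 4.5.4.** On the site inspection it says: "The visual inspection performed by the PI targets the integrity of the syringe barrel and the completeness of the syringe". Results go into four general rows: no structural issue and not functionally compromised, structural issue, functionally compromised, and both. Deficiencies are tabulated "for all the auto-injectors used and returned to the clinic" in seven categories: packaging, labelling, instructions, preparation, deployment, removal and other. The sponsor's technical assessment is not in the eCRF and is reported separately, as Protocol Table 3-1 also provides. SAP Table 4-1, which lists departures from the protocol, mentions no change to either endpoint.

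**The concern.** The trial is meant to show safe and effective use of the auto-injector, and these are its device-level results.

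A deficiency table limited to devices that were used and came back leaves out the cases in which a deficiency prevented use, or in which the device was lost after the problem was reported. Several of the table's own categories describe faults that arise before injection.

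The integrity table has a different gap. The needle lock is the only Table 8-1 control of the needle-protection mechanism, and participants keep devices used at home and bring them to the clinic (Protocol 6.1.1). If nothing directs the site to check the lock and no row is assigned to a failure, a reader of the study report cannot tell whether a low issue rate covers that failure mode.

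**Working it through.** **1. Deficiency table**

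Divide the investigator-reported deficiencies by what happened to the device: D1 on devices used and returned, D2 on devices not used, D3 on devices not returned.

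- Protocol endpoint: D1 + D2 + D3.
- SAP 4.5.4 table: D1.
- Shortfall: D2 + D3, or (D2 + D3) / (D1 + D2 + D3) of all reported deficiencies.

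The shortfall is zero only if no deficiency is reported on an unused or unreturned device. The documents anticipate both groups. SAP 4.2.2 counts injectors returned unused and gives lost, stolen and missing as reasons for a discrepancy between dispensed and returned. The schedule of assessments has deficiencies recorded at the telephone visits too, so one can be on record for a device that never comes back. No document gives D1, D2 or D3, so the fraction cannot be filled in.

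**2. Needle lock**

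| Table 8-1 control | Method in Table 8-1 | Named in SAP 4.5.4 for the site inspection? |
|---|---|---|
| Barrel integrity | Visual | Yes |
| Syringe empty | Visual | Yes (completeness of the syringe) |
| Needle lock | Qualitative | No; not named anywhere in the SAP |

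Three controls in the protocol, two in the SAP's description, one without a specified study output.

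Next, follow a device with an intact barrel, an empty syringe and an unlocked guard through the four SAP rows. The no-issue row also requires the device not to be functionally compromised. If the site notices the guard, the functional row is available, as is a deficiency category (deployment, removal or other). If the site looks only at the two named items, the no-issue row is where the device ends up. No rule settles which.

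**3. What the numbers can show**

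- Planned denominator: 25 participants × 14 self-administrations = 350, which reproduces the protocol's figure of approximately 350.
- With 0 issues in 350, the exact two-sided 95% upper limit is 1 − 0.025^(1/350) = 1.05%. SAP 4.5.4 plans only frequencies for this table, so this shows what a reader might compute. It is not a planned output.
- The documents give no lock-failure rate. Under assumed rates p, with independent devices, the expected number is 350p and the chance of at least one is 1 − (1 − p)^350:

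| Assumed p | Expected failures | Chance of at least one |
|---|---|---|
| 0.1% | 0.35 | 30% |
| 0.5% | 1.75 | 83% |
| 1% | 3.5 | 97% |
| 2% | 7 | 99.9% |

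These are counts of lock failures that might occur. They are not counts of misclassified devices, which would also need the proportion that the site fails to notice.

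**The case against.** The strongest reply is that the lock was deliberately left to the sponsor. Table 8-1 gives it a different method from the other two controls, the SAP's visual inspection covers exactly the two visual controls, and the table follows directly on the sponsor's assessment of every used device. Separate reporting of that assessment is planned in the protocol and disclosed. This reading is plausible and cannot be excluded. It does not remove the gap: Table 3-1 describes the sponsor's work as additional and outside the study results, so the study's own endpoint would lack this control without the SAP saying so.

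A reader might infer that a device with a failed needle guard must be tabulated as having no integrity issue. The documents do not support that. The four rows do not score individual controls, and the functional row and the deficiency categories are both open to such a device. Deficiencies also go onto a product quality complaint form that the sponsor investigates (schedule of assessments, footnotes).

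On the deficiency table, it can be said that SAP 4.1 lists all study data, SAP 4.5.4 lists device information, and SAP 4.2.2 counts unused returns. All true, but a listing does not put a deficiency into the endpoint count, and the SAP 4.2.2 counts do not tabulate reported deficiencies by category.

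Timing also matters. SAP Amendment 1 (05 March 2025) refers to observations made during the study, so a new eCRF item may come too late for devices already inspected and shipped.

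**Conclusion.** Both points hold in limited form.

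- **Deficiency table.** The restriction to used and returned devices conflicts with the protocol endpoint and is not listed as a change. Any deficiency reported on an unused or unreturned device is left out. This is the firmer of the two points, since it depends on no reading of Table 8-1.
- **Needle lock.** A lock-only failure has no specified check and no specified row, and may be tabulated as no issue. It is a risk created by silence; the SAP contains no rule that produces it.

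Neither can be sized. The lock-failure rates above are assumptions. It is tempting to conclude that a third of failing devices would be missed, since one control of three is absent, but nothing in the documents supports an even split of failures over the controls or a complete miss by the site. Both endpoints are descriptive and sit under other objectives. The primary endpoint of complete dose delivery is unaffected.

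**What to change.** **Deficiency table.** In SAP 4.5.4, tabulate every investigator-reported deficiency, with separate rows for devices used and returned, unused, and not returned. State the denominator, for example devices dispensed, which SAP 4.2.2 already counts. The cost is SAP wording and one reprogrammed table.

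**Needle lock.** State who applies each of the three Table 8-1 controls, and name the row of the integrity table that takes a lock failure. Where still feasible, collect the result with one pass/fail item in the existing site inspection. Where it is not feasible, footnote the table to say that it does not cover the needle lock and that this result is in the sponsor's separate report. The footnote costs one sentence. The added item costs an eCRF change and a short instruction to sites, and cannot recover devices already inspected and shipped.

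Merging the sponsor's results into the study table is technically possible ("Devices will be individually numbered for tracking purposes"), but it would reverse the protocol's plan to report them separately and is not needed to close the gap.

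Record both changes in the SAP amendment history.

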j The preinjection SIAQ (SIAQ PRE module version 2.1) will be completed preinjection at Visit 1; the postinjection SIAQ (SIAQ POST module version 2.1) will be completed directly following self-injection and no later than 30 minutes postinjection at Visit 1 and Visit 8 during the study Treatment Period.

k In accordance with the draft Food and Drug Administration Suicidal Ideation and Behavior Prospective Assessment of Occurrence in Clinical Trials

l Guidance (Food and Drug Administration, Guidance for Industry, 2012) study participants will be asked to complete the C-SSRS at study visits as specified.

m At Visits 1 and 8, the Investigator will observe the participant self-administering with the ZLP-AI device. The used ZLP-AI devices will be visually inspected by the Investigator to determine if the entire dose was completely delivered (ie, the yellow plunger that can be seen through the device window is completely depressed).

n All used AI devices will be sent to UCB for assessment of structural and mechanical integrity and damage (ie, clear evidence of damage/compromised structural integrity—not superficial, cosmetic imperfections).

o Note that ADEs, SAEs, ISRs, and medication errors can only be recorded on the 14 days that the participant is using the ZLP-AI, and device deficiencies will also be collected during those 14 days. Device deficiencies will be reported via the eCRF. In addition, sites will fill out a product quality complaint form; all product quality complaints will be investigated by UCB.

p A single PK sample will be collected **CC1**.

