### 9.4.2 Safety analyses

Safety endpoints are defined in [Table 3-1](#).

- SAEs, TEAEs, SAEs, and ADEs
  - An ADE is an AE related to the use of the AI device. An ADE includes: (1) Adverse event resulting from insufficiencies or inadequacies in the IFU, the deployment, the installation, the operation, or any malfunction of the device. (2) Adverse event that is a result of a use error or intentional misuse of the investigational device.
  - A SADE is an ADE that has resulted in any of the consequences characteristic of an SAE.
- Medication errors associated with adverse reaction
  - The definitions of medication errors can be found in Appendix 12 (Section [10.12](#)). The medication errors reported by the study participant (or, when appropriate, by a caregiver, or observed by the Investigator) will be recorded in the eCRF.
- Injection site reactions
  - Treatment-emergent injection site reactions.

Analyses of the safety data will be done on the SS population.

All AE data will be listed. Only TEAEs, ADEs, SAEs, and medication errors associated with clinical harm will be included in the summary tables. Treatment-emergent AEs are defined as AEs starting after the time of first injection in the study and up to and including 40 days after the final dose (or last contact in the study, depending on which occurs first).

All AEs will be coded and classified by system organ class, high level term, and preferred term according to the Medical Dictionary for Regulatory Activities.

In this study, safety reporting requirements apply to all constituents of the IMP (ZLP-AI combination product which includes: zilucoplan solution contained inside the PFS and the auto-injector housing the PFS) as per 21 CFR 320. Adverse events related to use of the ZLP-AI combination (ADEs) and device deficiencies will be summarized separately. Adverse events will be summarized by the frequency and percent of participants having 1 or more of the events in question. Planned summaries include overall AEs, AEs by intensity, AEs by relationship to study drug, SAEs, AEs leading to withdrawal, AEs leading to death, ADEs, SAEs, and AEs of special interest.

Vital signs and physical examination findings will be recorded in the eCRF only at Screening/Day 1. Clinically relevant changes in subsequent physical examinations will be recorded as AEs.

Physical examination findings at Day 1 will be listed. A by-participant listing of the C-SSRS questionnaire data will be provided.

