### 10.7.3 Definition of device deficiency

Device deficiency definition

 
• A device deficiency is an inadequacy of a device with respect to its identity, quality, durability, reliability, safety, or performance. Device deficiencies include malfunctions, use errors, and inadequate labeling.
 

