
 Evaluate the structural and mechanical integrity of the ZLP-AI after completion of self-administration 	
Other endpoints:
 
 Occurrence of used ZLP-AI combination products identified as having structural or mechanical integrity issues after completion of self-administration. Investigator observed and reported device deficiencies. Note: An independent assessment of the structural and mechanical integrity of all used ZLP-AI devices will additionally be performed by UCB. The outcome will be reported separately from the study results.

Table 1–1: Objectives and estimands/endpoints

Objectives	[Estimands/]Endpoints

 Evaluate the study participant's experience of self-administration with ZLP-AI as assessed by the SIAQ© 	
Other endpoints:
 
 Pre injection SIAQ (SIAQ PRE module) domain scores at Visit 1 Post injection SIAQ (SIAQ POST module) domain scores following self-administration using the ZLP-AI at Visit 1 and Visit 8

 Explore the study participant's preference for zilucoplan PFS (as used in MG0011 or commercial supply) vs ZLP-AI following the use of the ZLP-AI 	
Other endpoint:
 
 Patient Preference Question at Visit 8.

ADE=adverse device effects; gMG=generalized myasthenia gravis; IMP=investigational medicinal product; ISR=injection site reaction; PFS=prefilled syringe; PK=pharmacokinetics; SADE=serious adverse device effects; SAE=serious adverse event; SFU=Safety Follow-Up; SIAQ=Self-Injection Assessment Questionnaire; TEAE=treatment-emergent adverse event; ZLP-AI=zilucoplan-auto-injector
	

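### SAP 4.5.4 tabulates device deficiencies only for auto-injectors that were used and returned, a condition that the protocol's deficiency endpoint does not carry

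*SAP*

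**What the plan says.** **Endpoint.** Protocol Table 3-1 and SAP Table 1-1 list it among the Other endpoints as "Investigator observed and reported device deficiencies". It sits under the objective "Evaluate the structural and mechanical integrity of the ZLP-AI after completion of self-administration". The neighboring endpoint in the same row is worded "Occurrence of used ZLP-AI combination products identified as having structural or mechanical integrity issues after completion of self-administration", so that one is expressly tied to used devices.

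**Collection.** Protocol 6.1.1: "All device deficiencies (including malfunction use error and inadequate labeling) shall be documented and reported by the Investigator throughout the study". Protocol 10.7.3 gives the scope: "Device deficiencies include malfunctions, use errors, and inadequate labeling". A footnote to the schedule in protocol Table 1-1 adds that "device deficiencies will also be collected during those 14 days".

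**Planned summary in the protocol.** Section 9.4.2: "Adverse events related to use of the ZLP-AI combination (ADEs) and device deficiencies will be summarized separately". No filter on device status is given.

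**Planned summary in the SAP.** Section 4.5.4: "ZLP-AI deficiency as reported by the investigator will be summarized in frequency tables for all the auto-injectors used and returned to the clinic". Its categories include packaging, labeling and device preparation, alongside deployment and removal. It then plans a listing of device information without stating which devices the listing covers. In SAP 4.2.2, a used device is a self-administered one. SAP Table 4-1, which sets out departures from the protocol, is silent on this restriction.

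**The concern.** Whether a device enters the SAP table can depend on the deficiency itself. A device set aside because its packaging was damaged, its label was unreadable or it could not be prepared is not self-administered, so it is excluded. A device with a lesser fault that was still injected and handed back is included. Three of the seven SAP categories describe problems that can be found before injection, so the table can miss part of what it is meant to classify. Used devices that are lost, stolen or otherwise missing also drop out, for a different reason.

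The purpose of the study is to show safe and effective use of the auto-injector. A reader of the report would take this table as the count of deficiencies in the study.

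**Working it through.** **1. The plan's own figure.** Protocol 9.8 plans at least 25 participants and approximately 350 self-administrations. Protocol 4.1 gives 14 self-administrations each. 25 × 14 = 350, which reproduces. This is a count of injections. The documents do not state how many devices are dispensed.

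**2. Which devices reach the deficiency table.** SAP 4.5.4 is read with the SAP 4.2.2 meaning of used.

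| Device with a reported deficiency | Within the protocol endpoint wording | In the SAP 4.5.4 table |
|---|---|---|
| Used and returned | Yes | Yes |
| Attempted, injection failed, returned | Yes | Unclear; may be logged as used and malfunctioned |
| Used, not returned | Yes | No |
| Never attempted because of the defect | Yes | No |

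**3. Whether another SAP table recovers the last row.** SAP 4.2.2 splits used devices by malfunction, but counts returned unused devices as one number. A defective unused device is there, but cannot be told apart from a sound spare.

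**4. Illustration of size.** The counts are assumptions. Let *a* be deficient devices among 350 used and returned, and *u* be devices found deficient before use, each replaced. Each deficient device has one deficiency.

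- SAP rule: *a*/350.
- All reported deficiencies: (*a* + *u*)/(350 + *u*).
- Exact (Clopper-Pearson) 95% limits for *x*/*n*: the lower is the 0.025 quantile of Beta(*x*, *n* − *x* + 1), or 0 if *x* = 0. The upper is the 0.975 quantile of Beta(*x* + 1, *n* − *x*). For *x* = 0 and *n* = 350 the upper limit is 1 − 0.025^(1/350) = 1.05%.

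| *a* | *u* | SAP rule | All reported |
|---|---|---|---|
| 0 | 1 | 0/350 = 0% (0 to 1.05) | 1/351 = 0.28% (0.01 to 1.58) |
| 0 | 3 | 0/350 = 0% (0 to 1.05) | 3/353 = 0.85% (0.18 to 2.46) |
| 0 | 5 | 0/350 = 0% (0 to 1.05) | 5/355 = 1.41% (0.46 to 3.26) |
| 2 | 1 | 2/350 = 0.57% (0.07 to 2.05) | 3/351 = 0.85% (0.18 to 2.48) |
| 2 | 3 | 2/350 = 0.57% (0.07 to 2.05) | 5/353 = 1.42% (0.46 to 3.27) |
| 2 | 5 | 2/350 = 0.57% (0.07 to 2.05) | 7/355 = 1.97% (0.80 to 4.02) |

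If failed devices are not replaced, the figures move by less than 0.1 percentage point. For example, *u* = 3 with *a* = 0 gives 3/350 = 0.86% (0.18 to 2.48) against 0/347 = 0% (0 to 1.06). Each omitted device is worth about 1/350 = 0.29 percentage points.

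**The case against.** The best defense is the objective above the endpoint, which concerns integrity once the injection is finished. Limiting the summary to used devices is a defensible reading of it, so a reader who infers a flat contradiction goes too far. The broader reading has more support. The neighboring endpoint names used devices and this one does not, protocol 6.1.1 and 9.4.2 are unrestricted, and packaging and labeling categories fit poorly with a post-use-only count. The 14-day window limits time, not device status.

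Three stronger inferences are tempting, and the documents do not support them:

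- *Deficiencies vanish from the report.* SAP 4.1 plans listings of all study data, and 4.5.4 plans a device listing. The protocol also requires eCRF entry, a product quality complaint form (Table 1-1 footnote), reporting within 24 hours (8.3.8.3) and sponsor review of every deficiency (10.7.6). The loss is from a frequency table.
- *A device must have worked to be counted.* SAP 4.2.2 has a class for devices returned, used and malfunctioned, and keeps malfunctioned devices in its denominator. A failed attempt may be logged there. The sure losses are devices never attempted and used devices not returned.
- *A planned deficiency rate is biased toward zero.* No rate, denominator or confidence interval is specified for this endpoint. It is descriptive, neither primary nor secondary, and the study is not powered for any endpoint. The percentages and intervals above are not planned outputs.

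It is also fair to say that a denominator of dispensed devices alone would have its own fault, because unopened kits could dilute the rate.

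**Conclusion.** The mismatch stands. Followed as written, the SAP yields an incomplete summary of an endpoint that both documents word without that limit, and does so without declaring a change. The table can only miss deficiencies relative to the endpoint wording, so any error in the count is an understatement. Its size is unknown and is nil if no deficient device goes unused or unreturned. With one to five assumed pre-use failures, the share of devices with a deficiency would be understated by about 0.3 to 1.4 percentage points. With three such failures and no deficient used device, the SAP table would show none, and its upper 95% limit would be less than half the all-device limit (1.05% against 2.46%).

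The conclusion rests on reading used as self-administered in 4.5.4, as SAP 4.2.2 does, and on the endpoint wording prevailing over the objective above it. It is worth correcting before analysis, but it does not touch the primary endpoint.

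**What to change.** In SAP 4.5.4:

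1. Tabulate every investigator-reported deficiency by category, whatever the status of the device, split into used and returned, used and not returned, and not used.
2. State how a device that was attempted but failed is classed.
3. State the denominator. One option is devices used or attempted, plus any set aside for a deficiency so that every counted device is in its own denominator, with the dispensed number alongside.
4. Keep the used-and-returned base for the post-use structural integrity table only.
5. If the sponsor does intend a used-and-returned count, enter it in SAP Table 4-1 with a reason and state that the listing covers all reported deficiencies.

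No new data are needed, because the deficiency eCRF page and the accountability log already hold them. The cost is SAP wording and one more table split. The reported deficiency count may look slightly less favorable.
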